12.5.4 Mandatory reporting to Vaccine Adverse Event Reporting System

Per the FDA EUA for the Pfizer-BioNTech COVID-19 Vaccine, FDA EUA for the Moderna COVID-19 Vaccine, the FDA EUA for the Janssen COVID-19 Vaccine, the site investigator or designee is responsible for mandatory reporting of the following to the Vaccine Adverse Event Reporting System (VAERS) [48, 58, 59]:

- Vaccine administration errors, whether or not associated with an AE,
- SAEs (irrespective of attribution to vaccination),

- Cases of Multisystem Inflammatory Syndrome in adults and children, and
- Cases of COVID-19 that result in hospitalization or death.

Vaccination providers may report to VAERS other AEs that are not required to be reported.

The site investigator, or designee, is also responsible for recording vaccination information in the state/local jurisdiction's Immunization Surveillance System or other designated system.

12.5.5 Reporting of Adverse Events to Institutional Review Boards (IRBs)/Institutional Ethics Committees (IECs)

All investigators shall report AEs and SAEs, including expedited reports, in a timely fashion to their respective local IRBs and single IRB in accordance with applicable regulations and guidelines. All safety reports to the FDA shall be distributed by the Sponsor (DAIT/NIAID) or designee to the single IRB and all participating institutions for local IRB submission if required.

12.6 Pregnancy Reporting

The investigator shall be informed immediately of any pregnancy in a study participant. The investigator shall counsel the participant and discuss the risks of continuing with the pregnancy and the possible effects on the fetus. Monitoring of the pregnant participant shall continue until the conclusion of the pregnancy.

The investigator shall report to the SACCC all participant pregnancies within 1 business day of becoming aware of the event using the Pregnancy eCRF. The SACCC will report all pregnancies to DAIT/NIAID. All pregnancies identified during the study shall be followed to conclusion, and the outcome of each must be reported. The Pregnancy eCRF shall be updated and submitted to the SACCC when details about the outcome are available.

Information requested about the delivery shall include:

- Gestational age at delivery
- Birth weight, length, and head circumference
- Gender
- Appearance, pulse, grimace, activity, and respiration (APGAR) score at 1 minute, 5 minutes, and 24 hours after birth, if available
- Any abnormalities.

Should pregnancy complications result in an event meeting the SAE definition outlined in Section 12.2.6, such as congenital abnormality, birth defect, miscarriage, or medically indicated abortion, an SAE must be submitted to the SACCC using the SAE reporting procedures described above.

12.7 Reporting of Other Safety Information

An investigator shall promptly notify their local and central IRB, in accordance with applicable regulations and guidelines, as well as the SACCC and DAIT/NIAID via email when an “unanticipated problem involving risks to participants or others” is identified, which is not otherwise reportable as an AE.

12.8 Review of Safety Information

12.8.1 Medical Monitor Review

The DAIT/NIAID Medical Monitor shall receive monthly reports from the DAIT-SACCC compiling new and accumulating information on AEs, AESIs, SAEs, MAAEs, NOCMCs, and pregnancies recorded by the study site(s) on appropriate eCRFs.

In addition, the Medical Monitor shall review and make decisions on the disposition of the SAE and pregnancy reports received from the DAIT-SACCC.

12.8.2 DSMB Review

12.8.2.1 Planned DSMB Reviews

The progress of the study will be monitored by the NIAID DSMB. The NIAID Autoimmune DSMB is chartered to review safety data and to make recommendations to NIAID regarding continuation, termination, or modification of the study. The DSMB will review the safety data within 6 months after the first participant is treated, and an initial review should occur no later than after this first arm has closed to enrollment and all participants completed 4 weeks of follow up. Following the initial review, the DSMB will review the safety data approximately every 6 months during planned DSMB Data Review Meetings. Data for the planned safety reviews will include, at a minimum, a listing of all reported AEs, SAEs, MAAEs, NOCMCs, AESIs, and increases in autoimmune disease activity (flares/relapses).

The DSMB chair will be informed of any IND Safety Reports in a timely manner in order to make a recommendation for an ad hoc full board review and /or protocol suspension. In addition, safety data will be reviewed by the DSMB when an event occurs that is of sufficient concern to the NIAID medical monitor or protocol co-chairs to warrant review, or when an event occurs that could contribute to a stopping rule.

12.8.2.2 Ad hoc DSMB Reviews

12.8.2.2.1 Ad Hoc DSMB Reviews for Adult Participants

In addition to the pre-scheduled data reviews and planned safety monitoring, the DSMB may be called upon for ad hoc reviews. The DSMB will review any event that potentially impacts safety at the request of the protocol chair or DAIT/NIAID. Any of the following events will trigger an ad hoc DSMB Safety Review:

- Death related to vaccine
- Life-threatening AE (Grade 4) related to vaccine
- Permanent or severe disability related to vaccine
- Occurrence of a Grade 3 or higher, vaccine-related SAE of the same type in 3 or more of the study participants who have received a study treatment. *Note: Only SAEs occurring within 24 weeks of a Day 1 visit will be counted.*
- Occurrence of a Grade 2 or higher myocarditis or pericarditis within 6 weeks of vaccine administration. *Note: the DSMB chair will be notified within 3 business days from when the AESI is reported to DAIT/NIAID.*
- Occurrence of severe flare or relapse after an additional homologous COVID-19 vaccine dose given at Stage 1, defined as within 12 weeks of the Stage 1 Baseline/Week 0 visit (vaccination), in 3 of the first 10 participants or 30% thereafter, defined as follows.
- Occurrence of severe flare or relapse after a subsequent alternative COVID-19 vaccine dose given at Stage 2, defined as within 12 weeks of the Stage 2 Baseline/Week 0 visit (vaccination), in 3 of the first 10 participants or 30% thereafter.

Severe flare or relapse is defined as follows:

- **RA:** DAS28-CRP score >5.1.
- **SLE:** Severe score on the SELENA-SLEDAI flare index.
- **SSc:** Onset of new or significant worsening of internal organ involvement requiring hospitalization or change in treatment or worsening of skin thickening on the modified Rodnan skin score of >4 units [absolute change from screening visit].
- **MS:** Clinical relapse meeting either the criteria specified in (a) with investigator determination of relapse or the criteria in (a) **and** (b) below:

- a. Occurrence of new, recurrent or worsening neurological symptoms attributable to MS, that meet all of the following criteria:
 - i. Appeared or evolved subacutely (over <3 months).
 - ii. Persisting for >24 hours.
 - iii. Cannot be attributed to confounding factors (e.g., fever, infection, injury, poor sleep, adverse reaction to medication).
 - iv. Occur ≥ 30 days after the onset of a prior confirmed relapse.
- b. New, recurrent or worsening neurological symptoms accompanied by corresponding objective worsening on neurologic examination with an increase of any one of the following in MS participants compared to the immediate prior assessment:
 - i. ≥ 0.5 step(s) on the Expanded Disability Status Scale (EDSS), or
 - ii. ≥ 2 points on one Functional Systems Score (FSS), or
 - iii. ≥ 1 point on two or more FSS.

Episodic spasms, sexual dysfunction, fatigue, mood change, or bladder or bowel urgency or incontinence will not suffice to establish a relapse. Sexual dysfunction and fatigue will not contribute to the EDSS or FSS for assessing MS relapse.

- **Pemphigus:** 3 or more new lesions a month that do not heal spontaneously within 1 week or by the extension of established lesions in a participant who has achieved disease control.

After review of the safety data, the DSMB will make recommendations regarding study conduct, including modifications and/or continuation. The DSMB will recommend and DAIT/NIAID, as Sponsor, will determine whether protocol changes should be implemented and/or whether and when consenting, allocation, randomization, and vaccinations can resume.

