12.8.2.2.2 Ad Hoc DSMB Reviews for Pediatric Participants

In addition to the pre-scheduled data reviews and planned safety monitoring, the DSMB may be called upon for ad hoc reviews. The DSMB will review any event that potentially impacts safety at the request of the protocol chair or DAIT/NIAID. Any of the following events will trigger an ad hoc DSMB Safety Review:

- Death related to vaccine
- Life-threatening AE (Grade 4) related to vaccine
- Permanent or severe disability related to vaccine
- Occurrence of a Grade 3 or higher, vaccine-related SAE of the same type in 3 or more of the study participants who have received a study treatment. *Note: Only SAEs occurring between Day 1 and the Week 24 study visit will be counted.*
- Occurrence of a Grade 2 or higher myocarditis or pericarditis within 6 weeks of vaccine administration. *Note: the DSMB chair will be notified within 3 business days from when the AESI is reported to DAIT/NIAID.*
- Occurrence of severe flare or relapse after an additional homologous COVID-19 vaccine dose given at Stage 1, defined as within 12 weeks of the Stage Baseline/Week 0 visit (vaccination), in 3 of the first 10 participants or 30% thereafter, defined as follows.
- Occurrence of severe flare or relapse after a subsequent alternative COVID-19 vaccine dose given at Stage 2, defined as within 12 weeks of the Stage 2 Baseline/Week 0 visit (vaccination), in 3 of the first 10 participants or 30% thereafter.

Severe flare or relapse is defined as follows:

- **JIA:**

- a. JADAS10 >17 (polyarthritis, enthesitis-related JIA, and psoriatic arthritis), JADAS10 >13 (for oligoarthritis)
- b. PASI ≥12 (for psoriatic arthritis)
- **Pediatric SLE:** ≥ 6.4 on the SLEDAI-based ACR provisional criteria for global flares in childhood-onset SLE
- **JDM:** Decline in CMAS to <30 or JDM DAS>5
- **POMS:** Clinical relapse meeting either the criteria specified in (a) with investigator determination of relapse or the criteria in (a) **and** (b) below:
 - a. Occurrence of new, recurrent or worsening neurological symptoms attributable to MS, that meet all of the following criteria:
 - v. Appeared or evolved subacutely (over <3 months)
 - vi. Persisting for >24 hours.
 - vii. Cannot be attributed to confounding factors (e.g., fever, infection, injury, poor sleep, adverse reaction to medication)
 - viii. Occur ≥ 30 days after the onset of a prior confirmed relapse.

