$$\text{Fold improvement} = \frac{\text{anti-COVID-19 Antibody Response Week 4}}{\text{anti-COVID-19 Antibody Response Baseline}}$$

Longitudinal changes in the anti-COVID-19 antibodies will be summarized over time by study visit using descriptive statistics. Details on handling missing data and intercurrent events, which result in anti-COVID-19 antibody response data being unevaluable for immune response, will be outlined in the statistical analysis plan.

Longitudinal changes in neutralization and pseudoneutralization assays will be summarized by study visit using descriptive statistics. For secondary continuous efficacy endpoints, descriptive statistics will be used to summarize the distribution of scores in each arm; for adult participants, this will include the H-SLEDAI (SLE participants), Tender/Swollen Joint Count (RA participants), PDAI (pemphigus participants), modified Rodnan Skin Score (SSc participants), CGI-C, PtGA, PGI-C, PGA, and PROMIS 29, and for pediatric participants, this will include the SLEDAI-2K (SLE), Tender/Swollen Joint Count (JIA participants), MMT-8 and CMAS (JDM participants), CGI-C, PtGA, PGI-C, PGA, and PedsQL. The proportion of participants who meet definition for disease-specific flares, including the Thanou modified SELENA-SLEDAI Flare Index (SLE participants), patient-reported flare assessment (SSc participants), and physician-assessed relapse (MS participants), will be summarized. The disease-specific flare endpoints will include Thanou modified SELENA-SLEDAI Flare Index (SLE participants), DAS28-CRP (RA participants), patient-reported flare assessment (SSc participants), flare assessment (pemphigus participants) and physician-assessed relapse (MS participants) in adults and the ACR Provisional Criteria for Global Flare in Childhood-onset SLE (for SLEDAI; pediatric SLE participants), physician-assessed relapse (POMS participants), and flare assessment (JDM participants).

Descriptive statistics will be used to summarize the proportions of participants in the safety arm who experience safety endpoints.

For Stage 2, analysis plans for primary and secondary endpoints will be repeated to evaluate the immune response to a subsequent alternative COVID-19 vaccine dose and to determine whether immunologic variables are associated with increased disease activity.

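### Severe flare for RA, JIA and the JDM activity-score limb is a current score with no change required, so high activity already present before vaccination can count towards the DSMB flare trigger

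*Protocol*

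**What the plan says.** Protocol Sections 12.8.2.2.1 (adults) and 12.8.2.2.2 (pediatric) trigger an ad hoc DSMB review when severe flare or relapse within 12 weeks of vaccination reaches 3 of the first 10 participants, or 30% after that. Severe flare is then defined disease by disease.

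Level only, with no reference visit:
- RA: "DAS28-CRP score >5.1".
- JIA: "JADAS10 >17 (polyarthritis, enthesitis-related JIA, and psoriatic arthritis), JADAS10 >13 (for oligoarthritis"), or for psoriatic arthritis "PASI ≥12 (for psoriatic arthritis").
- JDM, second limb of "Decline in CMAS to <30 or JDM DAS>5".

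Change or new activity required:
- SSc skin score: more than 4 units, specified as "absolute change from screening visit".
- MS and POMS, criterion (b): an increase on EDSS or functional scores against the assessment just before.
- JDM, CMAS limb: a decline.
- Pemphigus: new lesions or extension of old ones.

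Under the eligibility criteria (Section 4.2), active disease excludes a participant only if it prevents the medication hold, leads to more or added immunosuppression during Screening, or suggests an MS relapse. The vaccination-day checks (Sections 8.1.3, 8.2.4 and 8.4.4) are built the same way. None sets a ceiling on DAS28-CRP, JADAS10, PASI or JDM DAS.

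Section 13.4.4 lists "DAS28-CRP (RA participants") among the flare endpoints. SAP 8.3.7.2 leaves the RA details to a later version.

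**The concern.** A safety trigger for flare after vaccination should count new or worsening disease. For the level-only limbs, a participant whose score is above the cut at Screening, stays there on unchanged therapy and is measured again at Week 4 or Week 12 satisfies the definition. For example, a DAS28-CRP of 5.5 before and after vaccination is a severe flare as written.

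Pre-existing high activity then adds to the numerator of the 3-of-10 and 30% rules. The DSMB may be called to review a signal that reflects case mix at entry. The fixed cut also errs the other way, because a large worsening that stays below it is not counted.

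**Working it through.** **Can a stably high participant reach the count?**
1. Entry: no score ceiling in any adult or pediatric eligibility list. Stable disease on unchanged therapy that permits the hold meets none of the active-disease exclusions.
2. Vaccination day: active disease blocks the dose only if it leads to more or added immunosuppression, or suggests an MS relapse.
3. Follow-up: the components of DAS28-CRP, JADAS10 and JDM DAS are scheduled at Weeks 4 and 12 (Tables 17 to 22), so the score is measured again inside the 12-week window.
4. Definition: the score exceeds the cut, so it counts.

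PASI has the same level-only wording but is partly gated. Section 8.3.4.2 and the pediatric schedules take it after Baseline only when a flare is suspected.

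**How much could this matter?** The documents give no error rate for the trigger, no background flare rate and no share above the cuts, so there is no plan figure to reproduce. All three inputs below are assumptions:
- f = 10%, true rate of new severe flare.
- s, share of counted participants with RA, JIA or JDM.
- q, share of those above the cut before vaccination and remaining there.

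Apparent rate p = f(1 − sq) + sq. The trigger probability is the binomial chance of at least 3 of 10. For the later limb, a single look at 60 participants (18 or more) is shown.

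| s | q | p | P(≥3 of 10) | P(≥18 of 60) |
|---|---|---|---|---|
| – | 0 | 0.100 | 7.0% | <0.1% |
| 30% | 10% | 0.10×0.97 + 0.03 = 0.127 | 12.4% | <0.1% |
| 50% | 20% | 0.10×0.90 + 0.10 = 0.190 | 29.2% | 2.7% |
| 50% | 30% | 0.10×0.85 + 0.15 = 0.235 | 42.9% | 15.0% |

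With no new flares at all (f = 0) and sq = 20%, the figures are 32.2% and 4.3%. If stable scores did not count, both would be zero.

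**Which stages?** Adult Stage 1 closed on 15 August 2022. If the last participant was screened by then, 28 days to vaccination plus 84 days of window ends about 5 December 2022, before protocol version 7.0 (13 December 2022). Adult Stage 2 and both pediatric stages remain.

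**The case against.** The strongest reply is that the protocol plainly means new activity, and several passages say so:
- Section 4.1 says patients with active disease at Screening are excluded.
- Section 6.7 bars vaccination during a flare at Baseline, in addition to the Section 8.1.3 conditions.
- Sections 12.4.2 and 12.8.2.1 treat flare as an increase in activity.
- The trigger itself speaks of occurrence after the dose.
- The synopsis limits triggers to events attributed to the vaccine.

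On this view the cut grades severity and does not replace onset.

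This settles the intention but not the rule. None of these passages is tied to the cuts. Sections 4.1 and 6.7 are broader than the criteria sites apply. The lead-in to Section 12.8.2.2.1 has no attribution limit, and flares of the qualifying disease are kept off the AE forms where attribution is recorded. If flare at Baseline were defined by the same cuts, most of the gap would close, but the protocol does not define it so.

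Other parts of the reply stand. The inputs above are assumed, and the later 30% limb moves much less than the first-10 look. The consequence is modest: the DSMB reviews and recommends, and Section 11.5 pauses new consent, allocation and randomization only if it has not met within two weeks. An over-sensitive review trigger errs towards caution. Baseline is also an awkward reference. It falls after the MTX or MMF/MPA hold has begun (Section 7.1.1), and DAS28-CRP or the pediatric joint count need not be repeated if Screening was under 10 days earlier.

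A reader might go further and infer that the RA flare endpoint in Section 13.4.4 already measures prevalence of high activity. The documents do not support that: the section names DAS28-CRP without adopting the 5.1 cut, Section 3.3 frames the endpoint as change in disease activity, and the SAP has yet to specify it. Nor do they support a claim that cross-disease flare comparisons are invalid, since none is planned; flares are summarised by disease.

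**Conclusion.** The definition is wrong as written for RA, for JADAS10 in JIA and for the JDM DAS limb, and to a lesser degree for PASI. Followed literally, it counts unchanged high activity as severe flare. This conclusion rests on the text alone.

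The direction is certain: trigger probability can only rise. The size is not, because it depends on how many participants enter above a cut, which neither document reports. The movement from 7% to roughly 12–43% for the first-10 rule is an illustration that assumes a 10% true flare rate, the stated shares, and persistence above the cut. The documents also do not say how many participants in the open stages have already passed that look. It would overstate the point to infer that the rule halts the trial. The change should be made, but it concerns the sensitivity of a review trigger.

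**What to change.** - Keep the existing cuts. State that for RA, JADAS10, PASI and JDM DAS a severe flare requires worsening from a named pre-vaccination assessment. Screening is one candidate: the SSc skin score already uses it, it precedes the hold, and DAS28-CRP, JADAS10 components and JDM DAS are collected then. PASI is first scheduled at Baseline, so that limb would need its Baseline value. For rollover participants screened by phone, name the earlier visit whose data serve as Screening.
- Have the protocol team state how participants already above a cut are counted, including what worsening qualifies, so that true worsening in them is not missed. The size of that worsening is a clinical decision for the team.
- Reconcile the definition with Sections 4.1 and 6.7 (active disease or flare at entry), Sections 12.4.2 and 12.8.2.1 (flare as an increase), and the vaccine-attribution wording in the synopsis.
- When SAP 8.3.7.2 specifies the RA flare summary, use the same change-based definition.

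The cost is an amendment to wording, one decision on participants already above a cut, and a matching SAP entry. No new assessment is needed.

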12.8.2.2.2 Ad Hoc DSMB Reviews for Pediatric Participants

In addition to the pre-scheduled data reviews and planned safety monitoring, the DSMB may be called upon for ad hoc reviews. The DSMB will review any event that potentially impacts safety at the request of the protocol chair or DAIT/NIAID. Any of the following events will trigger an ad hoc DSMB Safety Review:

- Death related to vaccine
- Life-threatening AE (Grade 4) related to vaccine
- Permanent or severe disability related to vaccine
- Occurrence of a Grade 3 or higher, vaccine-related SAE of the same type in 3 or more of the study participants who have received a study treatment. *Note: Only SAEs occurring between Day 1 and the Week 24 study visit will be counted.*
- Occurrence of a Grade 2 or higher myocarditis or pericarditis within 6 weeks of vaccine administration. *Note: the DSMB chair will be notified within 3 business days from when the AESI is reported to DAIT/NIAID.*
- Occurrence of severe flare or relapse after an additional homologous COVID-19 vaccine dose given at Stage 1, defined as within 12 weeks of the Stage Baseline/Week 0 visit (vaccination), in 3 of the first 10 participants or 30% thereafter, defined as follows.
- Occurrence of severe flare or relapse after a subsequent alternative COVID-19 vaccine dose given at Stage 2, defined as within 12 weeks of the Stage 2 Baseline/Week 0 visit (vaccination), in 3 of the first 10 participants or 30% thereafter.

Severe flare or relapse is defined as follows:

- **JIA:**

- a. JADAS10 >17 (polyarthritis, enthesitis-related JIA, and psoriatic arthritis), JADAS10 >13 (for oligoarthritis)
- b. PASI ≥12 (for psoriatic arthritis)
- **Pediatric SLE:** ≥ 6.4 on the SLEDAI-based ACR provisional criteria for global flares in childhood-onset SLE
- **JDM:** Decline in CMAS to <30 or JDM DAS>5
- **POMS:** Clinical relapse meeting either the criteria specified in (a) with investigator determination of relapse or the criteria in (a) **and** (b) below:
 - a. Occurrence of new, recurrent or worsening neurological symptoms attributable to MS, that meet all of the following criteria:
 - v. Appeared or evolved subacutely (over <3 months)
 - vi. Persisting for >24 hours.
 - vii. Cannot be attributed to confounding factors (e.g., fever, infection, injury, poor sleep, adverse reaction to medication)
 - viii. Occur ≥ 30 days after the onset of a prior confirmed relapse.
 - b. New, recurrent or worsening neurological symptoms accompanied by corresponding objective worsening on neurologic examination with an increase of any one of the following compared to the immediate prior assessment:
 - i. ≥ 0.5 step(s) on the EDSS scale, or
 - ii. ≥ 2 points on one Functional Systems Score (FSS), or
 - iii. ≥ 1 point on two or more FSS.

Episodic spasms, sexual dysfunction, fatigue, mood change, or bladder or bowel urgency or incontinence will not suffice to establish a relapse. Sexual dysfunction and fatigue will not contribute to the EDSS or FSS for assessing MS relapse.

After review of the safety data, the DSMB will make recommendations regarding study conduct, including modifications and/or continuation. The DSMB will recommend and DAIT/NIAID, as Sponsor, will determine whether protocol changes should be implemented and/or whether and when consenting, allocation, randomization, and vaccinations can resume.

